4.2.2 Definition of Baseline and Visit Time Windows

This observational study covers three documentation periods, see Figure 1. An overview of data to be collected throughout the study is summarized in Table 2.

Table 2 - Data Documentation Schedule

Assessment/ Procedure (only available data to be collected; no diagnostic or monitoring procedures to be applied to the patients apart from those of routine clinical practice)	Baseline	Treatment Period			Post-treatment (PT) Period		
		On-treatment visits	Mid treatment visit for pts receiving 24 weeks of therapy	EoT ^b	Early PT visit	SVR 12 visit	SVR 24 visit
Informed Consent	X ^a						
Demographic information	X						
IL28B	X						
Relevant CHC disease characteristics	X						
Liver fibrosis stage	X						
CHC treatment history	X						
HCV genotype and subtype	X						
HCV RNA samples	X	X	X	X	X	X	X
Clinical chemistry and hematology	X	X	X	X	X	X	X
ABBVIE REGIMEN initiation documentation	X						
ABBVIE REGIMEN adherence		X	X	X			
Concomitant medication	X	X	X	X			
Relevant medical history, co-morbidities	X						
sAE, AE and pregnancy reporting	X	X	X	X	X ^c	X ^d	X ^d
For patients receiving RBV: Evidence, in accordance with local label, that female patient or female partner of male patient is not pregnant	X						
Viral resistance sample	X			X		X	X
Patient questionnaires – PAM-13, BMQ 18-item	X			X			
PSP evaluation		X	X	X	X	X	

Abbreviations: EoT = End of Treatment (at Week 12 or 24 or at premature discontinuation),
PT = Post-Treatment

a Written informed consent must be obtained before any data documentation in the eCRF

b Patients who prematurely discontinue should return to the site to document EoT data

c Tolerability documentation until PT week 4

d Pregnancy reporting for patients treated with DAA plus RBV

In accordance with the non-interventional nature of the study all HCV RNA measurements will be performed at the sole discretion of the physician and all HCV RNA measurements have to be entered into the eCRF. All recorded HCV RNA values will be assigned to appropriate time points (baseline, on-treatment visits, EoT visit, post-treatment visits) as follows:

Table 3 - Analysis Time Windows for HCV RNA

Phase	Time point	Time Window
Pre-Treatment	Baseline	Last value prior to start of study treatment (i.e. \leq study day 1)
On-treatment		Study day during treatment period ^{^#} (Study day 1 = first treatment day)
Treatment Week	4 (RVR*)	15 - 42 [^]
EoT	Actual EoT	Study day of last dose# (28 days prior to last dose - 7 days post last dose)
Post Treatment	12 weeks (SVR 12 window)	\geq 70-126 days post last dose
	24 weeks (SVR24 window)	127-210 days post last dose

[^]values must also be \leq 7 days post last dose

\geq study day 2

*RVR = rapid virological response

All reported safety laboratory test results will be assigned to one of the time points using the time windows specified in the table below.

Table 4 - Analysis Time Windows for Safety Laboratory Data

Phase	Time point	Time Window
Pre-Treatment	Baseline	Last value prior to start of study treatment (i.e. \leq study day 1)
Treatment Weeks	4 (day 29)	Study day during treatment period (Study day 1 = first treatment day)
	8 (day 57)	15 – 42 [^]
	12 (day 85)	43 – 70 [^]
	16 (day 113)	71 – 98 [^]
EoT	Actual EoT	Study day of last dose# (28 days prior to last dose - 7 days post last dose)
Post Treatment	4 weeks (28 days post last dose)	8– 56 post last dose
	12 weeks (84 days post last dose)	57 – 126 days post last dose
	24 weeks (168 days post last dose)	127 – 252 days post last dose

[^]values must also be \leq 7 days post last dose

\geq study day 2

4.2.3 Handling of missing data

No data will be imputed for any effectiveness or safety analyses except for the analyses of the HCV RNA endpoints and certain PRO endpoints. The discussion of missing data imputation for the PRO endpoints is included in section 4.2.7.2.3.

HCV RNA values will be selected for an RVR, EOTR and SVR analysis based on visit windows as defined in Table 3. When there is no HCV RNA value in a visit window based on defined visit windows, the closest values before and after the window, regardless of the value chosen for the subsequent and preceding window, will be used for the flanking imputation described below. For analysis of RVR, EOT and SVR, if a subject has a missing HCV RNA value at a post-Day 1 visit but with undetectable or unquantifiable (\leq 50 IU/mL) HCV RNA levels at both the preceding value and succeeding value, the HCV RNA level will be considered undetectable or unquantifiable, respectively, at this visit for this subject. In addition, if a subject has an unquantifiable HCV RNA level at the preceding value and an undetectable HCV RNA level at the succeeding value, or vice versa, the HCV RNA level will be imputed as unquantifiable at this visit for this subject.

For analyses of RVR, subjects still missing a value for the visit after flanking imputation will be imputed as a failure. For EoTR and SVR analysis, if there is no value in the appropriate window after flanking imputation but there is an HCV RNA value after the window, then it will be imputed into the EoTR or SVR window respectively. Subsequent to this flanking imputation, if a subject is missing a value for the visit window associated with the analysis, the subject will be imputed as a visit failure (i.e., not undetectable or unquantifiable).

If a subject starts another treatment for HCV, then all HCV RNA values for this subject measured on or after the start date of the new HCV treatment will be excluded from analyses. The subject will be considered a failure for summaries of viral response at all time points after the start of the new HCV treatment.

Due to the non-interventional nature of this study several different methods for determination of the HCV RNA value can be applied. For the purpose of the statistical analysis, a HCV RNA measurement is considered ≤ 50 IU/mL,

- if a PCR test was used
- and the test result is undetectable and the LLoD of the test is ≤ 50 IU/mL or the test result is unquantifiable (i.e. detected but below LLoQ) and the LLoQ is ≤ 50 IU/mL.

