**Table 2 - Data Documentation Schedule**

Assessment/ Procedure (only available data to be collected; no diagnostic or monitoring procedures to be applied to the patients apart from those of routine clinical practice)	Baseline	Treatment Period			Post-treatment (PT) Period		
		On-treatment visits	Mid treatment visit for pts receiving 24 weeks of therapy	EoT b	Early PT visit	SVR 12 visit	SVR 24 visit
Informed consent	X a						
Demographic information	X						
IL28B	X						
Relevant CHC disease characteristics	X						
Liver fibrosis stage	X						
CHC treatment history	X						
HCV genotype and subtype	X						
HCV RNA samples	X	X	X	X	X	X	X
Clinical chemistry and hematology	X	X	X	X	X	X	X
ABBVIE REGIMEN initiation documentation	X						
ABBVIE REGIMEN adherence		X	X	X			
Concomitant medication	X	X	X	X			
Relevant medical history, co-morbidities	X						
sAE, AE and pregnancy reporting	X	X	X	X	X c	X d	X d
For patients receiving RBV: Evidence, in accordance with local label, that female patient or female partner of male patient is not pregnant	X						
Data on portal hypertension in patients with cirrhosis	X			X		X	X
Viral resistance sample	X			X		X	X
BMQ, PAM-13	X			X			
PSP evaluation		X	X	X	X	X	

Abbreviations: EoT = End of Treatment (at Week 12 or 24 or at premature discontinuation),  
PT = Post-Treatment

- a Written informed consent must be obtained before any data documentation in the eCRF
- b Patients who prematurely discontinue should return to the site to document EoT data
- c Tolerability documentation until PT week 4
- d Pregnancy reporting for patients treated with DAA plus RBV

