#### **9.4.1.5 Concomitant Medication**

**Concomitant medication** - the following will be documented:

- Concomitant medication used from the time when the decision is made to initiate treatment with the ABBVIE REGIMEN until after the last dose

It should be verified by the treating physician that concomitant medication can be safely administered with the ABBVIE REGIMEN (including ritonavir) and RBV. Some medications may be contra-indicated, some may require dose adjustments due to potential for drug-drug interactions (DDIs). The investigator or qualified designee should review the concomitant medication(s) labels and screen concomitant medications at each visit for potential DDIs.

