## **9.6 Data Management**

### **9.6.1 Electronic Case Report Forms**

Data for this study will be recorded in English by each participating center via an electronic data capture (EDC) system using a web-based eCRF. Examinations, diagnostic measures, laboratory assessments, findings and observations routinely performed in patients with CHC included in this cohort, will be transcribed by the investigator or designee from the source documents into the eCRF. Only data specified in the protocol will be entered into the eCRF. For each enrolled patient, the investigator or designee will create a new patient file in the eCRF and a unique patient number will be automatically allocated by the system.

A comprehensive data validation program utilizing front-end checks in the eCRF will validate the data. Automated checks for data consistency will be implemented, discrepancies need to be solved by the researcher in the eCRF before the module can be completed.

Follow-up on eCRF data for medical plausibility will be done by AbbVie personnel (or their representatives). Queries will be generated in the eCRF for online resolution at the site. The investigator or an authorized member of the investigator's staff will make any necessary data corrections to the eCRF. All change information, including the date and person performing the corrections, will be available via the audit trail, which is part of the EDC system. The principal investigator of each site will finally review the eCRFs for completeness and accuracy of available data and provide his or her electronic signature and date to the eCRFs as evidence thereof.

Access to the EDC system will be provided for the duration of the study through a password-protected method of internet access. Such access will be removed from investigator sites at the end of the site's participation in the study. Data from the EDC system will be archived on appropriate data media (e.g. CD-ROM) and provided to the investigator as a durable record of the site's eCRF data.

Original Questionnaires will be collected from the sites by Abbvie.

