## 9.7 Data Analysis

### 9.7.1 Analysis Population, Time Windows and Handling of Missing Data

The target population (TP) is defined as all patients who fulfill the criteria specified in Section 9.2.1. The core population (CP) is defined as all patients of the TP, who have started the treatment combination recommended in the current local label for their disease characteristics. Patients not receiving the treatment recommended in the local label will be summarized in the non-core population (NCP). In addition, the core population with sufficient follow-up data (CPSFU) is defined as all CP patients, who fulfil one of the following criteria:

- (1) evaluable HCV RNA data  $\geq 70$  days after the last actual dose of the ABBVIE REGIMEN (i.e. data within the SVR12 time window)
- (2) a HCV RNA value  $\geq 50$  IU/mL at the last measurement post-baseline (i.e. no virological response achieved at the last measurement on-treatment or post-treatment)
- (3) HCV RNA  $< 50$  IU/mL at the last measurement post-baseline, but no HCV RNA measurement  $\geq 70$  days after the last actual dose of the ABBVIE REGIMEN due to reasons related to safety (e.g. dropped out due to AE) or incomplete efficacy information (e.g. virologic failure such as relapse is reported in the eCRF but date and value of the corresponding HCV RNA test is missing). This means only patients who had virological response at their last on-treatment or post-treatment measurement, but had no HCV RNA measurements  $\geq 70$  days post-treatment for reasons not related to safety or effectiveness (e.g. lost-to-follow-up or patient not willing to perform an additional HCV RNA test  $\geq 70$  days post-treatment) will be excluded from this analysis.

The Safety Population (SP) is defined as all patients who received at least one dose of the ABBVIE REGIMEN.

In accordance with the non-interventional nature of the study all HCV RNA measurements will be performed at the sole discretion of the physician and all HCV RNA measurements have to be entered into the eCRF. All recorded HCV RNA values will be assigned to appropriate time points (baseline, on-treatment visits, EoT visit, post-

---

Confidential Information

No use or disclose outside AbbVie is permitted without prior written authorization from AbbVie

---

treatment visits). The time windows for the assignments will be specified in the statistical analysis plan (SAP).

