No data will be imputed for any effectiveness or safety analyses except for the analyses of the HCV RNA endpoints. When there is no HCV RNA value in a visit time window post-baseline, but prior to EoT, the closest values before and after the window, regardless of the value chosen for the subsequent and preceding window, will be used for the flanking imputation described below. If a patient has a missing HCV RNA value at a post-baseline visit prior to EoT but has undetectable HCV RNA (with LLoD  $\leq$ 50 IU/mL) or unquantifiable, but detectable HCV RNA levels (with LLoQ  $\leq$ 50 IU/mL) at both the preceding and succeeding measurements, the HCV RNA level will be considered undetectable or unquantifiable, respectively, at this visit for this patient. In addition, if a patient has an unquantifiable HCV RNA level at the preceding measurement and an undetectable HCV RNA level at the succeeding measurement, or vice versa, the HCV RNA level will be imputed as unquantifiable at this visit for this patient. For virological response at EoT a corresponding backward imputation approach will be applied. This means if HCV RNA is missing at EoT, then unquantifiable or undetectable will be assumed for EoT, if the succeeding HCV RNA value is undetectable or unquantifiable. For SVR12 the single last available HCV RNA measurement  $\geq$ 70 days post-treatment will be used. Subsequent to this flanking and backward imputation, if the HCV RNA value remains missing at a specific time point, then the patients will be considered as virological failure at this time point (i.e. not undetectable or unquantifiable).

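### SAP 4.2.3 depends on the start date of any new HCV treatment, but neither document provides for collecting it after end of treatment, so a retreated relapser can count as an SVR24 success and, less often, as an SVR12 success

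*SAP*

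**What the plan says.** **The rule.** SAP 4.2.3 deals with a patient who starts another HCV treatment in two steps. First, "all HCV RNA values for this subject measured on or after the start date of the new HCV treatment will be excluded from analyses". Second, "The subject will be considered a failure for summaries of viral response at all time points after the start of the new HCV treatment". The protocol has no corresponding rule.

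**What is collected.** Protocol 9.4.1.5 defines the medication to be documented: "Concomitant medication used from the time when the decision is made to initiate treatment with the ABBVIE REGIMEN until after the last dose". In Table 2 of the protocol, the row "Concomitant medication" is marked at baseline, on-treatment, mid-treatment and EoT, and at none of the three post-treatment visits. Table 2 in SAP 4.2.2 is the same. The post-treatment list in protocol 9.4.1.3 covers laboratory data, tolerability, portal hypertension, viral resistance and the PSP questionnaires, with no medication or retreatment item. Protocol 9.6.1 adds: "Only data specified in the protocol will be entered into the eCRF".

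**What continues to be collected.** Under protocol 9.7.1, "all HCV RNA measurements have to be entered into the eCRF", and Table 2 marks HCV RNA through the SVR24 visit.

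**How a missing SVR value is filled.** SAP 4.2.3 first tries flanking imputation. If the window is still empty but "there is an HCV RNA value after the window, then it will be imputed into the EoTR or SVR window respectively".

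**The concern.** The SAP rule is sensible, but it can only work if the analyst knows when a new HCV treatment began. After EoT the documents provide for the virological result and not for the fact needed to interpret it. If the date is missing, the exclusion does not operate, and an HCV RNA value below 50 IU/mL obtained on a different regimen is read as response to the ABBVIE REGIMEN.

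The error has one direction: a missing date can turn an intended failure into a success, never the reverse. At stake are SVR24, more marginally the primary SVR12 rate, and the few failures that carry the information in the predictor and adherence regressions.

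**Working it through.** **1. Is there another source for the date?** Two places in the SAP come close.
- The reasons for not completing the study (SAP 4.2.5) include post-treatment relapse. They apply to patients with no HCV RNA test from 10 weeks after treatment onward, and they carry no retreatment date.
- Co-medication profile B (SAP 4.2.8.2) covers a drug stopped before HCV treatment and resumed later. It does not cover a new HCV regimen, and no listed profile is for a drug first introduced after treatment.

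**2. Tracing patients through SAP 4.1.1, 4.1.2, 4.2.3 and Table 3 with the start date unknown.** Days count from the last dose. The SVR12 window is days 70 to 126 and the SVR24 window is days 127 to 210.
- *SVR24.* Below 50 at EoT, at or above 50 on day 84, retreated, below 50 on day 180. SVR24 requires only a value below 50 in its window and sets no condition on earlier response. Result: SVR12 failure, SVR24 success.
- *SVR12 by imputation.* Below 50 at EoT, at or above 50 on day 28, retreated from day 56, no test on days 70 to 126, below 50 on day 180. Flanking fails because the preceding value is not suppressed. The next step moves the day-180 value into the window. Result: success for both SVR12 and SVR24.
- *SVR12 directly.* Relapse before day 70, prompt retreatment, and a value below 50 on the new regimen inside days 70 to 126. Result: SVR12 success.
- *Two discordant values in the window.* The SAP does not say which one is used. Protocol 9.7.1 does: "For SVR12 the single last available HCV RNA measurement" at or after day 70, which would be the later, suppressed one.
- *Early discontinuation with response.* Protocol 9.2.3 asks for the SVR12 and SVR24 pages if data are available. If such a patient changes regimen, no relapse is needed for a value on the new regimen to count.

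**3. The plan's own figure.** Protocol 9.5 and SAP 3.2 give 417 evaluable patients at 90%. Clopper-Pearson with x = 0.90 × 417 = 375.3:
- lower limit = Beta quantile 0.025 (375.3, 42.7) = 86.71%
- upper limit = Beta quantile 0.975 (376.3, 41.7) = 92.71%

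The width is 6.00 points, as stated. For enrolment, 417 / 0.95 = 438.9, against 440 planned.

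**4. Size.** Each misclassified patient adds 1/417 = 0.24 points to SVR12; five add 5/417 = 1.20 points. The documents give neither the relapse share among failures nor a retreatment rate, so both are assumed:
- r, relapses as a share of failures: 25% to 75%
- m, share of relapsers who are retreated, suppressed in time and counted as successes: 5% to 25%

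With F failures (417 × 0.05 = 20.85, taken as 21; 417 × 0.10 = 41.7, taken as 42), bias = F × r × m / 417.

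| True SVR12 | F | r | m | Patients | Bias (points) |
|---|---|---|---|---|---|
| 95% | 21 | 0.25 | 0.05 | 0.26 | 0.06 |
| 95% | 21 | 0.75 | 0.25 | 3.94 | 0.94 |
| 90% | 42 | 0.25 | 0.05 | 0.53 | 0.13 |
| 90% | 42 | 0.75 | 0.25 | 7.88 | 1.89 |

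All four lie below the planned CI half-width of 6.00 / 2 = 3.00 points.

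**The case against.** **The eCRF is not available.** Whether the date is captured is settled there. The sentence in protocol 9.6.1 is not a reliable guide, because the SAP analyses items that the protocol does not list: alcohol units per week (4.2.6.4), the method of documenting adherence (4.2.7.2.1) and the co-medication profile scheme (4.2.8.2). Profile B itself presupposes some medication information from after treatment. This stands. A reader might infer that the date is not collected; the documents support only that neither of them specifies its collection. Nor does 9.4.1.5 set a precise end, since it runs until after the last dose. The cut-off at EoT comes from Table 2.

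**The route into the primary endpoint is narrow.** Under the SAP's 126-day limit, a patient whose only in-window value is 50 IU/mL or more stays an SVR12 failure. A false success needs early relapse with fast retreatment, an empty window, or two discordant values. This also stands, and it is why SVR24, a secondary endpoint reported in its own CPSFU population, is the more exposed. The protocol's open-ended last-value rule would be more permissive, but the SAP openly replaces it with the 70-to-126-day window.

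**Relapses do not vanish.** The viraemic value stays in the data, and the separate relapse analysis (SAP 4.2.7.2.1) could still count the patient. That limits the loss, but it also means that the relapse and response tables could disagree about the same patient.

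**The size rests on assumptions.** Ten patients, or 10/417 = 2.40 points, is easy to quote. At a true 95% it would require 10 of 21 failures (48%) to be retreated, suppressed and missed, and nothing in the documents supports that.

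**Conclusion.** The point holds as a gap between an analysis rule and the data specified to run it. It is more than a missing detail. Followed literally, SAP 4.2.3 moves a later suppressed value into an empty SVR12 window despite documented post-treatment viraemia, and the SVR24 definition accepts a suppressed value whatever came before.

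The effect on SVR12 is upward and probably small: 0.24 points per patient, and about 0.06 to 0.94 points at a true 95% or 0.13 to 1.89 at a true 90%, on the assumed r and m. No comparable range was worked out for SVR24, where the route is easier.

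A reader might conclude that the primary result will be inflated by retreated patients. The documents do not show that: they give no retreatment rate, and an existing eCRF field cannot be ruled out. The change is still worth making, because the SAP already relies on the date. By the protocol's milestones, data collection was to run to August 2018, well after the SAP date of 22 November 2016.

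**What to change.** 1. **Collect the date, or name its source.** Add one item to protocol 9.4.1.3 and Table 2 at the early post-treatment, SVR12 and SVR24 visits: new anti-HCV treatment started (no/yes), drug, start date. If the eCRF already holds this, naming the field in SAP 4.2.3 is enough. Query it retrospectively for every patient with any HCV RNA of 50 IU/mL or more at or after EoT, and for every early discontinuation. The query is the only part that reaches discontinuers who change regimen without viraemia.
2. **Add a default to SAP 4.2.3.** After a post-EoT HCV RNA of 50 IU/mL or more, a later value below 50, whether imputed into or measured within the SVR12 or SVR24 window, does not count as response unless absence of retreatment is documented. The rule has to cover measured values, because blocking imputation alone leaves the direct SVR12 route and the SVR24 route open.

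Cost: a short protocol amendment, one eCRF item, a few site queries and one SAP sentence. Patients undergo no added procedure and the sample size does not change. The reported SVR rates may come out slightly lower, because a patient with post-treatment viraemia whose retreatment status cannot be established would count as a failure.
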